#### **7.1.1.4 Assessment of Intensity**

Intensity refers to the degree of discomfort or impairment associated with an event. The intensity of MEs/AEs is to be reported on the eCRF. To maximize consistency in assessment, the National Cancer Institute (NCI) Common Terminology Criteria for Adverse Events (CTCAE) scale is to be used.

#### **7.1.1.5 Serious Adverse Events**

An SAE is an adverse event occurring at any dose that results in any of the following outcomes:

- Death
- A life-threatening adverse event
- Inpatient hospitalization or prolongation of existing hospitalization
- A persistent or significant disability or incapacity
- A congenital anomaly in the offspring of a patient who received the study treatment
- An important medical event that does not result in death, is not life-threatening, and does not necessitate hospitalization but which in the investigator's judgment may jeopardize the patient and may necessitate medical or surgical intervention to prevent one of those outcomes. Examples include allergic bronchospasm requiring intensive treatment in an emergency room or at home, blood dyscrasias or convulsions that do not result in inpatient hospitalization, or the development of drug dependency or treatment-related substance abuse.

Clarifications:

- "Life-threatening" means that the patient was, in the view of the investigator, at immediate risk of death from the event as it occurred. This definition does not include an event that, had it occurred in a more severe form, might have caused death.
- Hospitalization for elective treatment of a pre-existing condition that did not worsen during the study is not considered an AE.
- Complications that occur during hospitalization are AEs. If a complication prolongs hospitalization, the event is considered an SAE.
- "Inpatient" hospitalization means the patient has been formally admitted to a hospital for medical reasons. This may or may not be overnight. It does not include presentation at a casualty or emergency room unless the event meets one of the other criteria for being an SAE.

- With regard to the criteria for an important medical event, medical and scientific judgment should be used in deciding whether prompt reporting is appropriate in this situation.

#### **7.1.1.6 Reporting of Serious Adverse Events**

All SAEs occurring up to 30 days following completion of or discontinuation from the study must be reported to the sponsor, regardless of whether they are suspected of having a causal relationship with the study drug. Any SAEs for which the investigator does suspect a causal relationship must be reported to the sponsor regardless of the time elapsed since the last dose of the study drug.

Patients will be instructed to report SAEs to the investigator **within 24 hours**, by telephone. In turn, the investigator must report all SAEs to the sponsor **within 24 hours** of occurrence or notification by the patient, using the sponsor's SAE form. The sponsor will provide contact information for reporting SAEs. An assessment of causality must be provided at the time of the initial report. In the case of an SAE that is fatal or life-threatening, the investigator or delegate must then complete and submit a follow-up SAE form to the sponsor **within 5 calendar days**, and must submit further follow-up forms if additional relevant follow-up information becomes available.

The sponsor will submit reports of SAEs to the appropriate regulatory agencies, in line with local regulatory requirements and timelines.

Investigators must report all SAEs to their IRB/IEC as well as to the sponsor. If any SAE that is considered at least possibly related to the study medication and is unexpected occurs at one site, the sponsor will promptly inform all other sites of this, and all investigators must then report this event to their own IRBs/IECs, following the same timelines as above or following local IRB/IEC policy, whichever takes precedence.

#### **7.1.1.7 Follow-up and Documentation of SAEs**

SAEs that occur during the study and up to 30 days after the last dose of study drug must be documented in the patient's medical record and on the SAE report form. The investigator should attempt to establish a diagnosis of the event based on signs, symptoms, and/or other clinical information. In such cases, the diagnosis rather than the individual signs/symptoms should be documented as the SAE.

All SAEs must be followed until resolution, the condition stabilizes, the event is otherwise explained, or the patient is lost to follow-up. The investigator is responsible for ensuring that follow-up includes any supplemental investigations that may be indicated, in order to elucidate the nature and/or causality of the SAE as completely as possible. This may include additional laboratory tests or investigations, histopathological examinations, or consultation

with other health care professionals. The sponsor may request that the investigator perform or arrange for the conduct of supplemental measurements and/or evaluations.

If a patient dies during participation in the study or during a specified follow-up period, the sponsor should be sent a copy of any post-mortem findings, including histopathology.

New or updated information is to be recorded on the originally completed SAE report form, with all changes signed and dated by the investigator.

The clinical research associate (CRA) will verify the original SAE report form against the source documents at the next monitoring visit.

### **7.1.1.8 Adverse Events of Special Interest**

#### **7.1.1.8.1 Elevated Liver Enzymes**

Due to the rate of elevated levels of ALT and AST seen in healthy volunteers in study LA60-0118, particular attention will be paid to these measures in the current study to determine if their rates are higher than expected in patients with systemic iron overload. Investigators are to review all laboratory reports promptly, and are to report any increases in ALT or AST that meet the criteria described in [Section 3.1.1](#) to the sponsor within 24 hours of occurrence, using the sponsor's SAE form.

#### **7.1.1.8.2 Neutropenia**

Individuals taking deferiprone must be monitored for neutropenia, defined as a confirmed absolute neutrophil count (ANC) less than  $1.5 \times 10^9/L$ . Categories of neutropenia are as follows:

Mild:	A confirmed ANC $< 1.5 \times 10^9/L$ but $\geq 1.0 \times 10^9/L$
Moderate:	A confirmed ANC $< 1.0 \times 10^9/L$ but $\geq 0.5 \times 10^9/L$
Severe / agranulocytosis:	A confirmed ANC $< 0.5 \times 10^9/L$

For a case of neutropenia to be confirmed, there must be 2 consecutive counts, a maximum of 3 days apart, that are both less than the specified value. If the 2 counts are not in the same severity category, a third count will be required to determine the severity. If a patient has just a single ANC value less than  $1.5 \times 10^9/L$  this is to be documented in the eCRF as an AE of "decreased ANC", but is not to be defined as neutropenia. The investigator is to use judgment as to whether the decrease is clinically significant.

In addition to having ANC monitored, patients will be advised to immediately report any symptoms indicative of infection such as fever ( $\geq 38.5^\circ C$ ), sore throat, and flu-like symptoms at any time during treatment or during the first week following treatment. They will be

provided with an emergency services card with contact information, and advised to carry it with them at all times.

Depending of the severity of neutropenia, patients will either remain in or be withdrawn from the study. The management of different severities of neutropenia is described below.

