Diagnosis and main criteria for inclusion:	
Main inclusion criteria
 
 
• Male or female aged <math>\geq 18</math> years
 
• Diagnosis of thalassemia syndrome, sickle cell disease, or other disorder requiring a regular regimen of red blood cell transfusions
 
• On a stable regimen (<math>\geq 3</math> months) of Ferriprox tablets for the treatment of systemic iron overload
 
• A record of at least the last 12 measured ALT and AST levels prior to baseline
 
 
Main exclusion criteria
 
 
• ALT and/or AST value <math>> 5 \times</math> ULN at screening
 
• Active case of hepatitis B or C at screening
 
	
Investigational product:	
Product: Deferiprone delayed release (DR) 1000 mg tablets
 
Dose: All patients will receive deferiprone DR at approximately the same total daily dosage at which they were taking Ferriprox (Group A: closer to 75 mg/kg/day; Group B: closer to 100 mg/kg/day), approximately 12 hours apart, rounded to the nearest 500 mg half-tablet
 
Mode of administration: Oral
	
Schedule of treatment and specimen collection:	
Schedule of Treatment
 
Patients will receive 28 days of b.i.d. dosing with deferiprone DR tablets.
 
 
• Biochemistry: Screening and Days 3, 7, 14, 21, and 28
 
• Hematology: Screening, baseline, and Days 7, 14, 21, and 28
 
• Coagulation: Screening and Day 28
 
• Serology: Screening
 
	

Name of Sponsor: ApoPharma Inc.	Individual Study Table	(For National
Name of Finished Product: Deferiprone delayed release tablet	Referring to Part of the	Authority Use Only)
Name of Active Ingredient: 3-hydroxy-1,2-dimethylpyridin-4-one	Dossier Volume: Page:	

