#### **3.1.1.1 Criteria for Safety Concerns**

As a consequence of liver iron overload and frequent blood transfusions, patients in the target population may have fluctuations of AST and/or ALT that frequently exceed the reference ranges. In recognition of this variability, for each of these enzymes, the criteria for deciding whether an individual patient's increases during the current study is of concern will be set as follows:

- For a patient whose baseline level is within the normal range, the criterion will be reaching a value of 5 times the ULN during the study.
- For a patient whose baseline level is above the ULN, the criterion will be reaching a value of 5 times the baseline value during the study or 10 x ULN.

All cases of patients meeting either of the above criteria at any point during the study must be reported to ApoPharma by the investigator within 24 hours of occurrence, using the sponsor's SAE form.

If at any time during the study a patient's ALT and/or AST values reach a level of **10 x ULN**, do the following:

- If the patient is symptomatic and/or has any other clinically significant abnormal laboratory results, immediately withdraw the patient from the study.
- If the patient is asymptomatic and has no other clinically significant abnormal laboratory results, interrupt treatment and obtain a confirmatory count the next day.
  - If the value is confirmed to be  $\geq 10$  x ULN:
    - Stop treatment, withdraw the patient and complete all end of study assessments scheduled for Day 28
    - Document the event and report it within 24 hours to ApoPharma
    - Monitor the patient daily until the elevated value returns to a level that is regarded as not clinically significant
  - If the confirmatory value is found to be  $< 10$  x ULN, resume treatment as per protocol, and monitor liver enzyme levels within 3 days of resuming therapy.

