##### **4.5.1.2 Neutropenia**

A sudden drop in absolute neutrophil count (ANC) is a reaction that has been associated with deferiprone treatment and is considered an adverse event of special interest. ANC values will be monitored throughout the study. For a case of mild, moderate, or severe neutropenia to be confirmed, there must be 2 consecutive counts of ANC, a maximum of 3 days apart,

that are both less than a specific value. If at any time, a patient's confirmed ANC level is found to be below  $< 1.5 \times 10^9/L$ , the investigator is to do the following:

- *Mild neutropenia:* If the confirmed ANC is  $< 1.5 \times 10^9/L$  but  $\geq 1.0 \times 10^9/L$ , continue treatment without interruption, but monitor ANC every 2 days until resolution.
- *Moderate neutropenia:* If the confirmed ANC is  $< 1.0 \times 10^9/L$  but  $\geq 0.5 \times 10^9/L$ , interrupt treatment and monitor ANC every 2 days until resolution. The patient should re-initiate treatment once the event is resolved. If ANC is still  $< 1.5 \times 10^9/L$  after 14 days, withdraw patient from the study and monitor until resolution of the event.
- *Severe neutropenia / agranulocytosis:* If a single ANC is  $< 0.5 \times 10^9/L$ , immediately interrupt treatment without waiting for confirmation of the count and obtain a second measurement the following day. If the second ANC is still  $< 0.5 \times 10^9/L$ , permanently withdraw the patient from the study and follow the procedures for the management of agranulocytosis.

Details on the management of each category of neutropenia are provided in [Section 7.1.1.8.2](#).

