**Day 28 ( $\pm 2$  days) or Early Termination**

- Collect blood samples for assessment of the following:
  - Biochemistry
  - Hematology
  - Coagulation
  - Pregnancy testing (women of childbearing potential only)
- Collect a urine sample for urinalysis. Microscopic examination must be performed if dipstick test is outside the reference range for leukocyte, blood, nitrite or protein. (Note: for patients with sickle cell disease, samples are to be sent for microscopy if there is blood in the urine or three or more “plus signs” for protein.)
- Perform a symptom-oriented physical examination (to be completed by the principal investigator or a qualified delegate)
- Measure vital signs (heart rate, blood pressure, and body temperature).
- Review information that has been noted by the patient about doses taken, concomitant medications, and adverse events
- Collect medication containers
- Verify treatment compliance through tablet count and review of information in the patient’s notes
- Collect information on any adverse events that have occurred since the previous contact

- Collect information on concomitant medications
- Administer questionnaire on the acceptability of deferiprone DR vs. that of Ferriprox

If deemed necessary, patients with ongoing laboratory-related events may be asked after the last dose to provide further blood samples until resolution.

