All AEs must be followed until resolution, the condition stabilizes, the event is otherwise explained, or the patient is lost to follow-up. The investigator is responsible for ensuring that follow-up includes any supplemental investigations that are needed to elucidate the nature and/or causality of the AE as completely as possible. This may include additional laboratory tests or investigations, histopathological examinations, or consultation with other health care professionals.

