**Mild and moderate neutropenia:**

A patient who develops mild neutropenia is to continue treatment without interruption, but ANC is to be monitored every 2 days until resolution.

A patient who develops moderate neutropenia is to interrupt treatment as soon as the neutropenia is confirmed, and ANC is to be monitored every 2 days until resolution.

The patient should re-initiate treatment once the event is resolved, defined as 2 consecutive  $ANC \geq 1.5 \times 10^9/L$ . If ANC is still  $< 1.5 \times 10^9/L$  after 14 days, the investigator is to do the following:

- Withdraw patient from the study and monitor him/her until resolution of the event
- Advise patient regarding protective isolation
- Examine patient the same day (if possible), including drug history and physical examination
- Notify ApoPharma Inc. using the SAE form

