**Severe neutropenia/agranulocytosis:**

A patient in whom a single ANC measurement  $< 0.5 \times 10^9/L$  is detected is to immediately stop treatment, without waiting for confirmation of the count, and a second measurement is to be done the following day. If the second ANC is still  $< 0.5 \times 10^9/L$ , the patient is to be permanently withdrawn from the study, and ANC is to be monitored daily until resolution. The following procedures should be done by the investigator or the treating physician, as appropriate:

- Provide protective isolation; if clinically indicated, admit patient to hospital and obtain vital signs every 4 hours
- Examine the patient the same day, if possible, including drug history and physical examination
- Notify ApoPharma Inc. using the SAE form.

The following additional measures describe a suggested medical management and monitoring:

- If possible, consider obtaining bone marrow aspirate for:
  - Histology
  - Progenitor culture
  - Frozen storage (1 mL sample)
- If possible, consider obtaining bone marrow biopsy (minimum length 3 mm)
- Perform septic work-up including chest X-ray, blood, urine, and throat cultures
- Obtain q4h temperatures from patient (monitored by family at home if patient is not in the hospital)
- If warranted, administer granulocyte stimulating factors, such as G-CSF 10 µg/kg, on an in-patient basis if possible, beginning the same day that the ANC is confirmed as  $< 0.5 \times 10^9/L$ ; administer daily until ANC is  $> 1.5 \times 10^9/L$  on 2 consecutive days
- If ANC  $< 0.5 \times 10^9/L$  for 7 days, repeat bone marrow biopsy and aspirate weekly during the period of agranulocytosis, if warranted

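### No timed repeat ANC is ordered after a single asymptomatic count of 0.5 to <1.5 x 10^9/L, so the moderate-neutropenia rule can wait a week or never formally trigger

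*Combined protocol and SAP*

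**What the plan says.** Neutropenia is an adverse event of special interest. For any grade to be confirmed, Section 4.5.1.2 states that "there must be 2 consecutive counts of ANC, a maximum of 3 days apart", both below the relevant threshold; Section 7.1.1.8.2 repeats the definition. The mild step (continue, ANC every 2 days) and the moderate step (interrupt, ANC every 2 days) are both written for a confirmed ANC. On moderate cases, Section 7.1.1.8.2 says: "A patient who develops moderate neutropenia is to interrupt treatment as soon as the neutropenia is confirmed".

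A patient with only one count below 1.5 x 10^9/L gets an AE entry of decreased ANC, "but is not to be defined as neutropenia. The investigator is to use judgment as to whether the decrease is clinically significant".

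The Synopsis gives the sampling schedule: "Hematology: Screening, baseline, and Days 7, 14, 21, and 28". The windows are ±1 day at Day 7 and ±2 days at Days 14, 21 and 28.

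The protocol does order a timed repeat in two neighboring situations. After a single ANC below 0.5, treatment stops "without waiting for confirmation of the count, and a second measurement is to be done the following day". For asymptomatic ALT/AST at 10 x ULN, Section 3.1.1.1 tells the site to "interrupt treatment and obtain a confirmatory count the next day". Symptoms of infection also trigger an ANC (Sections 4.5.1.3 and 7.1.1.8.3).

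**The concern.** The definition presupposes an unscheduled second count, but no sentence instructs the site to obtain one within 3 days for an asymptomatic ANC of 0.5 to <1.5. A site that follows the text can wait for the next weekly sample. That sample will usually fall outside the 3-day limit too, so even a second low value would not confirm the event.

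Confirmed mild neutropenia continues on treatment anyway. The treatment step at risk of delay is therefore interruption for an asymptomatic count of 0.5 to <1.0. Section 1.3 justifies the weekly count as a means of early detection, and that purpose is weakened if the response depends on a confirmation nobody is told to seek. There is also a classification problem: the number of confirmed mild and moderate cases may be too low, and would depend on which sites choose to repeat early.

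**Working it through.** The plan states no figure on this point, so the check is whether the scheduled counts can satisfy the plan's own confirmation rule.

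**Inputs.** Post-dose hematology on Days 7, 14, 21 and 28, and the visit windows (Table 5.1, Section 7.1.2); 3-day confirmation limit (Sections 4.5.1.2 and 7.1.1.8.2); b.i.d. dosing from Day 1 to Day 28 (Table 5.1); 30 patients (Section 4.1).

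**Permitted sampling days.** Day 6–8, Day 12–16, Day 19–23, Day 26–30.

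**Gaps.** Shortest gap = earliest day of the later visit minus latest day of the earlier visit; longest gap = the reverse. All whole-day pairs were then enumerated.

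| Interval | Nominal | Shortest | Longest | Pairs with gap ≤3 days |
|---|---|---|---|---|
| Day 7 to 14 | 7 | 12 − 8 = 4 | 16 − 6 = 10 | 0 of 3 x 5 = 15 |
| Day 14 to 21 | 7 | 19 − 16 = 3 | 23 − 12 = 11 | 1 of 5 x 5 = 25 |
| Day 21 to 28 | 7 | 26 − 23 = 3 | 30 − 19 = 11 | 1 of 5 x 5 = 25 |

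Total: 2 of 65, or 2/65 = 3.1%. This is a share of permitted day pairs, not a probability, since real visits cluster near the nominal day. At nominal timing no pair qualifies.

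**Doses taken while waiting.** Nominal: 7 x 2 = 14. Widest Day 14 to 21 gap: 11 x 2 = 22, which needs visits on exactly Days 12 and 23. With an ordered 3-day repeat: at most 3 x 2 = 6.

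**Illustration.** A patient with an asymptomatic ANC of 0.7 at nominal Days 7, 14 and 21 has three counts in the moderate range, each 7 days apart. None is confirmed under the definition, so the interruption rule never formally applies.

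**After Day 28.** No further count is scheduled. The Day 28 visit text in Section 5.1 says only that, if deemed necessary, "patients with ongoing laboratory-related events may be asked after the last dose to provide further blood samples until resolution". The patient meanwhile returns to the regular chelation regimen (Section 3.1).

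**Other text that might supply the order.** Section 7.1.2 lets the investigator increase the frequency of evaluations for a clinically significant AE, and Section 3.1.1.2 permits repeat tests within the liver-enzyme enrollment rules; neither is an instruction. The third count in Section 7.1.1.8.2 applies only once two counts exist.

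**The case against.** The strongest reply is that a repeat is implied. Patients must be monitored for neutropenia, neutropenia is defined by two counts at most 3 days apart, and weekly sampling cannot deliver that without an extra draw. On this reading, the sentence about a single low value merely labels a count whose repeat was normal. There is also a real follow-up duty. A single low ANC is an AE, and Section 7.1.1.2 says "All AEs must be followed until resolution, the condition stabilizes, the event is otherwise explained, or the patient is lost to follow-up", with the investigator responsible for including any further tests needed. Many sites would repeat promptly. What remains is that none of this sets a deadline: a count at the next weekly visit arguably meets the follow-up duty and still misses the 3-day limit. Where the protocol wants a prompt repeat, it says so and gives the timing.

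Some of the reply limits the point. Counts below 0.5 and symptomatic patients are covered by firm rules. For a low count first seen at Day 28, study dosing is ending, so little or no interruption of the DR tablets can be delayed; AEs are collected for 30 days after the last dose, and Section 3.1 allows further samples over that time. The Day 28 gap therefore concerns mainly classification and follow-up. Single low counts are still recorded as AEs, and abnormal safety data are tabulated (Section 9.4.1.3), so the raw information is not lost. Neutropenia is neither the primary nor a secondary endpoint.

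The number affected is probably small. Section 1.3 gives about 6.4% for neutropenia on Ferriprox, mild and moderate together, over an unspecified exposure. Applied crudely to 30 patients, that is 30 x 0.064 = 1.9. It is not a 28-day rate, and participants have already been on Ferriprox for at least 3 months with a screening ANC of at least 1.5.

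**Conclusion.** The concern holds. As written, an asymptomatic ANC of 0.5 to <1.5 carries no timed repeat, although the mild and moderate steps depend on one, and the scheduled counts almost never meet the 3-day limit. The consequence for treatment is confined to the 0.5 to <1.0 band: a nominal 7 days on drug, at most 11 between scheduled counts while dosing continues, against at most 3 with an ordered repeat. These figures assume a site that does only what the text requires. The documents give no 28-day neutropenia rate, so no number of affected patients is claimed. The primary endpoint and sample size are unaffected. The change should be made because it concerns patient safety in an adverse event of special interest and costs very little, but it does not threaten the trial's main result.

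**What to change.** Add one sentence to each of Sections 4.5.1.2 and 7.1.1.8.2, and a hematology footnote to Table 5.1: after any single ANC below 1.5 x 10^9/L, obtain an unscheduled repeat within 3 days, including when the low count is first seen at Day 28 or early termination. Keep the next-day rule for counts below 0.5, and leave the treatment steps for each severity as they are.

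The alternative, lengthening the 3-day limit so that weekly counts can confirm, needs no extra blood but keeps moderate-range patients on drug longer.

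Cost: the plan has 30 x 4 = 120 scheduled post-dose counts. If 1% to 10% were low (an assumption, since the documents give no rate), that is 120 x 0.01 = 1.2 to 120 x 0.10 = 12 extra counts, which local laboratories can do. The confirmation definition already presupposes these draws.
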